Description of Agent or Intervention:	
Arm 1: Usual care + immediate ventilatory support for a maximum of 7 days. Brain death or death will be considered a failure of the primary intervention.
 
Arm 2: Usual care + infusion of 3% hypertonic saline to achieve a blood sodium concentration of 150-160 mmol/L. Ventilatory support will be provided to patients who experience a respiratory arrest, and this will be considered a failure of the primary intervention.
 
Arm 3: Usual care (elevation of the head of the bed 30 degrees and intravenous antimalarial drugs). Ventilatory support will be provided to patients who experience a respiratory arrest, and this will be considered a failure of the primary intervention.
 
Final outcomes will be determined at 7 days post-randomization: The primary study outcome will be recovery vs treatment failure, where treatment failure is a composite of death, ventilatory rescue (Arms 2 and 3), and brain death

Objectives:

Primary Objective

Compare final outcomes in pediatric CM patients receiving usual care (Arm 3) with both of two interventions (Arm 1 and Arm 2).

Secondary Objectives:

[figure not shown]
1. Among survivors of this interventional study, compare rates of adverse neurological outcomes in those assigned to the two interventions and those assigned to usual care.
2. Among all children admitted to the Paediatric Research Ward and screened for eligibility for randomization, evaluate and validate biomarkers of increased brain volume.
3. Assess the safety of early mechanical ventilation as well as intravenous hypertonic saline in children with CM.
4. Establish association between specific pathogenic mechanisms and TCD-derived phenotypes.

Description of Study Design:

Prospective, randomized, controlled non-blinded clinical trial

Estimated Time to Complete Enrollment:

Six years

PICU¹: will be on continuous monitoring 24hrs, then transferred to PRW

²pts in Arms 2 and 3 who experience respiratory arrest will be placed on ventilators.

³Treatment failure is a composite of death, ventilatory rescue or brain death

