2.3 Rationale

This clinical trial of adjuvant therapy (immediate ventilatory support, or hypertonic saline) for Malawian children with CM is directed toward the supportive treatment of increased brain volume, and it avoids the pitfalls that have bedeviled previous trials because:

- The interventions target a mechanism recently recognized as being strongly associated with a fatal outcome, severely increased brain volume; this mechanism is self-limited in CM survivors, suggesting that supportive care or rescue therapy may be effective.

The clinical trial setting in Malawi has been transformed because, beginning in July 2017, mechanical ventilation became available in the new Paediatric Intensive Care Unit (PICU) at the Queen Elizabeth Central Hospital.

This introduces new ethical issues: mechanical ventilation cannot be withheld in patients who suffer a respiratory arrest, and ventilatory support may result in a cadre of survivors with severe neurological sequelae. Therefore, “treatment failure” (failure of the primary intervention) is defined differently in the different therapeutic arms. In Arms 2 and 3, in which participants are not randomized to immediate ventilatory support, any participants who suffer respiratory arrest and are placed on ventilators *or* who die *or* are brain dead will be classified as treatment failures. In Arm 1, the patients who are randomized to receive immediate ventilatory support, “treatment failure” is defined as brain death at any time, *or* death at 7 days, with ventilatory support withdrawn.

The hypothesis underlying this prospective, randomized clinical trial is that death in children with CM occurs when raised intracranial pressure from severely increased brain volume impairs the function of the medullary respiratory center and that interventions which reduce ICP or support ventilation will improve survival rates in CM patients.

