11.4 Outcomes

The primary endpoint is death within one week following randomization. In Arm 2 and Arm 3, the endpoint will include failure of the initial treatment allocation such that the patient requires rescue ventilation. Several secondary outcomes will be assessed in the trial. Table 8 gives a brief description and preferred analytic strategies. Additional details are provided elsewhere in the Protocol.

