11.6 Interim Analyses

The TBS design is a 4-stage sequential plan to compare VENT to UC on the outcome of mortality. Based on historical controls and initial randomization to UC before 2020, mortality is

assumed fixed at $p_0 = 0.28$. We test the hypothesis that mortality p in VENT is lower, i.e., we test $H_0 : p = p_0$ versus $H_1 : p < p_0$ at significance level $\alpha = .05$. VENT will be declared superior to UC, if we can demonstrate a relative risk reduction of 50% with 80% power. This needs a sample of 38 subjects.

Boundaries for the 4-stage plan are derived from the power family. Early stopping is to reject the null hypothesis. Our first interim analysis was conducted with data from the 2019-2020 malaria seasons. Observed mortality in VENT was 12.5% (2/16). The conclusion was to continue to the next stage. Our current estimate, at the end of the 2021 season is 15.8% (3/19). In accordance with the design, we must continue to the next stage (i.e., 2022 season). The revised boundary information is depicted in the figure.

Figure: Boundary plot at conclusion of stage 2

Legend: The scale is the maximum likelihood estimate (MLE) of the mortality difference (PDIFF), $\theta = p - p_0$ against the actual information level. At stage 1, observed $\theta = 0.125 - 0.28 = -0.155$, and at stage 2, $\theta = 0.158 - 0.28 = -0.122$. The rejection boundaries are not crossed.

Conditional power and predictive power

Conditional power (CP) is the power to reject the null hypothesis $H_0: \theta = 0$ at all future stages given the cumulative interim data. This calculation shows: (a) at the current estimated difference in mortality $\theta = -0.122$, CP=76.1%, (b) at zero difference in mortality, CP=18.6%, (c) at the hypothesized difference, $\theta = -0.14$, CP=82.9%. Predictive power (PP) is the posterior probability

of rejecting the null at the next stage given the current data, assuming a non-informative prior on the mortality difference. PP=66.1% at the current stage.

Based on these assessments it behooves that we proceed to stage 3.

Hypertonic saline (HPS) vs UC

We have our first sample of 3 subjects, one of whom died. Although hardly necessary, a formal analysis provides the exact 95% CI for mortality in HPS, (0.008, 0.906).

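### The interim and primary test for VENT use a mortality count (3/19 against 28%) that does not match the stated primary outcome (5/19 dead or brain dead, controls also put at 36%)

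*Combined protocol and SAP*

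**What the plan says.** **Endpoint.** The Protocol Summary says for Arm 1: "Brain death or death will be considered a failure of the primary intervention". Section 2.3 says that treatment failure in Arm 1 "is defined as brain death at any time", or death at 7 days. Section 3.2.1 gives a composite that includes brain death, and Section 4 gives one that includes severe irreversible neurologic failure. Section 11.4 differs: "The primary endpoint is death within one week following randomization". It adds rescue ventilation for Arms 2 and 3 and does not mention brain death.

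**Test.** Section 11.6: "The TBS design is a 4-stage sequential plan to compare VENT to UC on the outcome of mortality". Section 11.7 takes the primary test from this design.

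**VENT counts.** Section 11.6 uses 2/16 at stage 1 and, at stage 2, "Our current estimate, at the end of the 2021 season is 15.8% (3/19"). Section 4 gives 26.3% at the end of 2021, being five of 19 dead or brain dead. Section 11.5 gives 25% for VENT, which would be 4/16, although no count is printed.

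**Control rate.** Section 11.6: "Based on historical controls and initial randomization to UC before 2020, mortality is" assumed fixed at 0.28. Sections 4 and 11.5 give 36%; Section 4 derives it explicitly from historical controls plus randomised usual care. All three call it mortality, and none explains the gap.

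**Reading.** Section 11.6.1 sees promise in VENT and no evidence of futility. Section 4 expects VENT to be declared futile later.

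**The concern.** The final primary analysis inherits its event and its null value from Section 11.6. If that event is death alone, a VENT child who is brain dead could count as a non-event in the primary test, although four other places in the protocol call that child a treatment failure. The decision to continue VENT at stage 2 also rests on conditional and predictive power calculated for the narrower event.

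The control rate has its own difficulty. The 48 historical controls were scanned in 2014-2017. Section 2.3 says "beginning in July 2017, mechanical ventilation became available in the new Paediatric Intensive Care Unit (PICU"), and Section 4 records the unit as still under construction in 2017. Rescue ventilation was therefore largely unavailable to the historical controls, whereas the 16 randomised usual-care children could receive it. A composite control rate that pools the two groups needs a stated event rule, and there is none.

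**Working it through.** **Inputs.** One-sided alpha 0.05, 80% power, p0 = 0.28 and a 50% reduction (Section 11.6); control rate 36% (Sections 4 and 11.5); VENT 3/19 (Section 11.6) and 5/19 (Section 4). Final VENT size: 38 in Section 11.6, 33 in Section 11.5, and 19 + 7 + 6 = 32 in the projected-enrollment table of Section 4.

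**Sample size.** With the variance at the alternative, n = p1(1 − p1) × [(1.645 + 0.8416)/(p0 − p1)]² = 0.14 × 0.86 × (2.4866/0.14)² = 37.98. This matches "This needs a sample of 38 subjects".

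**Conditional power (CP).** Let p̂ be the observed VENT rate at n = 19, p1 = p0/2, and θ the size of the assumed reduction.

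- I = n/[p̂(1 − p̂)], Imax = N/[p1(1 − p1)], t = I/Imax
- Z = (p0 − p̂)√I
- CP = Φ{[Z√t + θ√Imax(1 − t) − 1.645]/√(1 − t)}

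**Reproducing the plan (3/19, p0 = 0.28, N = 38).** I = 19/(0.158 × 0.842) = 142.9; Imax = 38/(0.14 × 0.86) = 315.6; t = 0.453; Z = 0.122 × √142.9 = 1.46. At the trend the numerator is 0.982 + 1.187 − 1.645 = 0.524; divided by √0.547 = 0.740 this is 0.709, so CP = 76.1%. The three values are 76.1 / 18.5 / 82.7%, against the stated 76.1 / 18.6 / 82.9%. Predictive power comes to 68.3% against the stated 66.1%, so it is close but not exact.

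**Same method with 5/19.** I = 19/(0.263 × 0.737) = 98.0.

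- p0 = 0.28, N = 38: t = 98.0/315.6 = 0.310; Z = 0.0168 × 9.90 = 0.167.
- p0 = 0.36, N = 38: Imax = 38/(0.18 × 0.82) = 257.5; t = 0.381; Z = 0.0968 × 9.90 = 0.959.

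| VENT count, p0, N | CP at trend | CP at zero | CP at 50% reduction |
|---|---|---|---|
| Stated in 11.6 | 76.1% | 18.6% | 82.9% |
| 3/19, 0.28, 38 | 76.1% | 18.5% | 82.7% |
| 5/19, 0.28, 38 | 5.3% | 3.1% | 57.8% |
| 5/19, 0.28, 32 | 4.2% | 2.6% | 44.9% |
| 5/19, 0.36, 38 | 45.4% | 9.0% | 82.5% |
| 5/19, 0.36, 32 | 38.4% | 8.8% | 72.9% |
| 3/19, 0.36, 38 | 99.2% | 59.2% | 98.5% |

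Of the four count and p0 pairings at N = 38, only 3/19 with 0.28 gives the stated figures. Predictive power for 5/19 at N = 38 is 18% (p0 = 0.28) or 47% (p0 = 0.36).

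**Sensitivity.** A single common variance (null, observed or alternative) with critical values 1.645 to 1.705 gives, for 5/19 at N = 38, a trend CP of 2-3% (0.28) or 26-45% (0.36). At the 50% reduction it gives 19-36% or 54-79%. At N = 32 the trend range for 0.36 is 19-37%. The lowest values come from the null variance, which does not reproduce the plan: for 3/19 against 0.28 it gives 51.8 / 12.7 / 58.6%. Four-stage power-family boundaries with the reproducing method give a trend CP at N = 38 of 2-5% (0.28) or 30-43% (0.36).

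**Size of the data conflict.** The exact one-sided p at stage 2 is 0.178 for 3/19 against 0.28, 0.552 for 5/19 against 0.28, 0.266 for 5/19 against 0.36, and 0.049 for 3/19 against 0.36.

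**The case against.** The best defence is that two consistent sets of figures have become mixed. Section 11.5 introduces the primary outcome as death or failure of the intervention before giving 36% and 25%. On that reading 36%, 25% and 5/19 are failure rates, and 28%, 12.5% and 3/19 are deaths. With 64 controls the percentages fit 23/64 and 18/64, though neither count is printed. The right pairing for the stated outcome would then be 5/19 against 0.36, where CP is 45 / 9 / 83%, and the Section 11.6.1 statement that the evidence does not point to futility would stand.

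This is plausible, and it is a reason not to treat 5/19 against 0.28 as the correct pair. It does not remove the problem. The primary test in Section 11.7 would still be on the narrower event, both control rates would still be called mortality, and CP at the trend would still be 45% rather than 76%.

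A reader might infer the opposite: that with p0 = 0.28 the trial's futility guide is met and VENT should stop. The documents do not support that. The guide in Section 11.6.1 is advice taken from the literature (CP below, for example, 20% over a plausible range of effects), and the range is not defined. Under the method that reproduces the plan, CP at the design effect is 45-58% for N = 32 to 38 even with 0.28. It is below 20% only for true reductions smaller than about 7 percentage points. Settings that put it below 20% at the design effect use variance or boundary choices that fit the stated figures less well.

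The Section 4 expectation of futility is also a forecast that defers to the formal assessment. It is in tension with Section 11.6.1 but is not a second, contradictory result.

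**Conclusion.** The conflict of endpoint, VENT count and control rate is in the current operative text and governs the primary test. The stated CP belongs to 3/19 against 0.28 and does not apply to the stated primary outcome. On 5/19, CP at the observed trend falls from 76% to about 5% (p0 = 0.28) or 45% (p0 = 0.36) at 38 children. With the reproducing method, whether it lies below 20% at the trend depends on p0. At a 50% reduction that method gives more than 20% under both values. Futility therefore cannot be scored as met or not met, and the claim of promise is not established for the stated outcome.

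Two links are inferences. No section labels 3/19 as deaths only, and Section 4 itself calls the 5/19 figure a mortality risk. No section says that 36% is a wider failure rate. A different time window could also explain the two extra VENT children, since Section 2.3 counts brain death at any time, Section 11.4 says one week, and Section 4 gives no window for 5/19. The CP values are approximate: the boundary figure is not available, and one final critical value stands in for the remaining stages. Confidence is high for the conflict and moderate for the exact percentages.

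**What to change.** 1. Use one primary endpoint in Sections 3.2.1, 4, 11.4, Table 8, 11.5, 11.6, 11.6.1 and 11.7, with brain death counted for VENT as Sections 2.3, 3.2.1 and 4 already have it. If death alone is kept for the test, amend those sections and report death or brain death alongside it.
2. Tabulate death, brain death and rescue within 7 days by arm, with historical controls and randomised usual care shown separately. Note that rescue was largely unavailable to the 2014-2017 controls, and state how the event is defined for them.
3. Explain 28% against 36%, with counts, and derive p0 on the same event definition as VENT. The p-value of 0.818 in Section 4 should be checked at the same time: for 5/19 against 23/64 (an assumed count), chi-square gives 0.44, with continuity correction 0.62, and Fisher's test 0.58.
4. Restate stages 1 and 2 with confirmed counts. Settle the VENT sample size (38, 33 or 32) and recompute the boundaries, conditional power and predictive power before the next look.
5. Define the plausible range of effects in the futility guide, and reconcile the Section 4 forecast with Section 11.6.1.

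The cost is a wording amendment, one table from data already held, and one re-run of the interim calculation. The re-run may move the reading for VENT in either direction.

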11.6.1 Futility Analysis

Futility Analysis: Although VENT seems an effective treatment, does it promise at this stage *substantial benefit* compared to UC? To answer this question we calculated the *conditional power* to reject the null hypothesis at all future stages give the current interim data. Conditional power (CP) is calculated on hypothesized values of the alternative θ . Our current value is –0.122. CP at the current value is 76.1%. At the hypothesized difference, $0.14 - 0.28 = -0.14$, CP=82.9%. These do suggest promise of VENT. However, if the true difference in mortality is actually zero ($\theta=0$) then CP=18.6%. The literature advises that if CP is small (e.g., <20%) over a plausible range of θ values, then it would be *futile* to continue the trial. *The evidence that we have now does not point to futility.*

11.7 Statistical Analysis

For the primary outcome, the test of the null hypothesis $H_0 : \theta = 0$ vs $H_1 : \theta < 0$ for the mortality difference $\theta = p - p_0$ follows from the sequential design described in 11.6. The preferred analytic method for secondary outcomes by type/scale is included in Table 8. The unit of analysis is the individual child (indexed by i) with a single outcome measure Y_i and covariates \mathbf{x}_i which includes an indicator for treatment arm (VENT, HPS, UC), socio-demographic and clinical variables whose prognostic influence on the outcome is of interest or needs to be controlled. The ensuing data on the N children are $\{(Y_i, \mathbf{x}_i) : 1 \leq i \leq N\}$. We expect $N=128$ across all three arms. Depending on whether the early stopping and futility rules are triggered in 11.6, sample size will vary by treatment arm. Minimum size in UC is 64 if no new recruitment into this arm is made in 2022 and 2023. Minimum size in HPS is 32, and in 21 in VENT if futility is triggered. With these caveats we describe broadly our statistical analyses.

Analysis of binary outcomes in Table 8 is by logistic regression. Continuous variables such as optic nerve sheath diameter on admission, heart rate variability patterns, and opening CSF pressure on admission are analyzed using linear models. To mitigate the effects of skewness in their distributions, if found, a logarithmic or square-root transformation g will be applied to Y_i and analysis carried out on the transformed variable. To assess the effect of treatment on outcome we will fit the linear model $E(g(Y_i) | \mathbf{x}_i) = \mathbf{x}_i' \beta$ and test the hypothesis $H_0 : \beta_1 = 0, \beta_2 = 0$ where β_1 and β_2 are the coefficients for the VENT and HPS, respectively. Point estimates and

associated 95% confidence intervals for response mean on the original scale will be calculated and would involve smearing.²⁶⁰⁻²⁶²

For assessments made serially over time, the outcome is a vector $\mathbf{Y}_i = (Y_{i1}, Y_{i2}, \dots, Y_{im})'$ of repeated continuous (e.g., sheath diameter on admission and then twice daily) or repeated binary indicators (e.g., severe neurologic sequelae at 1, 6 and 12 months). Generalized linear models $g(E(Y_{ij} | \mathbf{x}_i)) = \mathbf{x}'_j \beta + \mathbf{z}'_j \mathbf{b}_i$ are apropos with right hand side covariates specific to the j -th time, \mathbf{z}_j will include an intercept and terms involving time permitting assessment of the evolution of the mean outcome (or probability for binary outcomes) over time, both within-subject and across the study population (i.e., population average). The link g is the identity function for continuous responses, and the logit for binary responses. Correlations between components of \mathbf{Y}_i are incorporated via the random effects. A judicious choice of covariance structure for \mathbf{b}_i will be elicited from information criteria.²⁶³⁻²⁶⁵ Alternating logistic regression will be considered the case of binary responses.²⁶⁶ Repeated ordinal measures (e.g., brain volume) will be analyzed by proportional odds or partial proportional odds models.^{267,268}

In all analytic procedures we will examine the overall goodness-of-fit, and presence of influential and/or outlying data points with graphical techniques and formal residual analyses.

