3 OBJECTIVES

3.1 Study Objectives

Primary Objective

Compare final outcomes in pediatric CM patients receiving usual care (Arm 3) with both of two interventions (Arm 1 and Arm 2).

Secondary Objectives:

1. Among survivors of this interventional study, compare rates of adverse neurological outcomes in those assigned to the two interventions and those assigned to usual care.
2. Among all children admitted to the PRW with CM whose parents consent to screening, evaluate and validate biomarkers of increased brain volume.
3. Assess the safety of early intubation and mechanical ventilation as well as intravenous hypertonic saline in children with CM.
4. Establish association between specific pathogenic mechanisms and TCD-derived phenotypes.
 - a. microvascular obstruction phenotype with MRI findings
 - b. hyperemia phenotype with hypercapnia on blood gas analysis, acidosis, and seizures on EEG
 - c. vasospasm phenotype with regional EEG findings of loss of fast frequencies and increased slow frequencies in territories of affected vessels and MRI findings with localized ischemic changes
 - d. low flow phenotype with compromised hemodynamics, diminished compensatory reserve and increased brain volume per MRI

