8.2 Laboratory Evaluations

8.2.1 Clinical Laboratory Evaluations

Approximately three mls of blood will be obtained at admission, and a fingerpick blood sample will be taken every 6 hours for the next 48 hours. Fingerpick samples will be approximately 200 μl in volume, resulting in an approximate total blood volume obtained of 3.6 mls.

An evaluation of malaria parasitemia (MP) and hematocrit (packed cell volume (PCV)) will be performed at initial screening and every six hours thereafter. These exams will continue until two consecutive examinations show an absence of malaria parasites. MP evaluation is performed on a thick blood smear. PCV is determined in a microhematocrit tube.

Lumbar puncture: A lumbar puncture will be attempted at the time of admission on all children admitted to the PRW, and if successful, the opening pressure (mm CSF) will be recorded. This is performed to eliminate meningitis as an alternate etiology of coma. Cerebral spinal fluid (CSF) will be sent for cell count, differential, and culture. 1 ml of the total 4 ml volume will be archived for subsequent studies of biomarkers of increased brain volume.

Respiratory swab: All participants will have a nasopharyngeal swab collected at the time of admission. These will be batch analyzed (after hospitalization) to detect respiratory viral pathogens.

Red Blood Cell (RBC) Cryopreservation: RBCs will be cryopreserved and sent to an outside institution for bio-banking/future analysis.

Blood for culture will be obtained on all participants admitted to the PRW. Blood will be obtained from either a peripheral or femoral vein and transferred to a pediatric BacTec bottle for subsequent analysis.

Plasma for archive: One ml of blood will be collected in a lithium heparin anticoagulated tube. Plasma will be separated and archived for subsequent studies of biomarkers of increased brain volume.

Urine for archive: Urine will be collected either while inserting an indwelling urinary catheter *or* by attaching a sterile urine collection bag to the perineum, and at least one ml will be archived for subsequent studies of biomarkers of increased brain volume.

Blood glucose levels will be measured using point of care testing on admission and every 6 hours thereafter until the participant has maintained a BCS of 3 for greater than 4 hours. Machines will be checked for accuracy each morning with a manufacturer supplied test strip.

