11.5 Sample Size and Power

For the primary outcome death/failure of the intervention, we conduct two parallel studies: (i) VENT versus control UC, (ii) HPS versus control UC. Approximately 128 children will be enrolled in the studies. This includes the 64 children in UC comprised of 16 randomized to UC in the 2018-2019 malaria seasons and augmented by 48 historical controls from previous seasons (2014-2017). We also randomized 16 children to VENT in the 2018-2019 malaria seasons.

Table 8: Summary of outcome measures and analytic plan		
Outcome measure	Outcome type/scale	Analytic method
PRIMARY OUTCOME		
Success of primary intervention or survival in the first 7 days after randomization	Binary	Logistic regression
SECONDARY OUTCOMES		
Brain volume determination (MRI on admission, then daily)	Ordinal	Ordinal regression
Optic Nerve Sheath Diameter (on admission, then daily)	Continuous	Linear regression. Serial assessments by repeated measures analysis
Transcranial Doppler ultrasound (on admission, then daily)	Continuous	Linear regression. Serial assessments by repeated measures analysis
Opening CSF pressure (mm CSF) (on admission)	Continuous	Linear regression
Heart rate variability patterns	Continuous	Linear regression. Serial assessments by repeated measures analysis
Neurologic exam * (on admission, then twice daily)	21 binary and 5 continuous variables	Linear or logistic regression
Papilledema (on admission, then daily)	Binary	Logistic regression
Severe neurologic sequelae at 16 and 12 months	Binary	Logistic regression. Serial assessments by repeated measures analysis
Hypotension that occurs within 30 minutes of sedation administration, initiation of mechanical ventilation or ventilator pressure adjustment.	Binary	Logistic regression.

Since the beginning of this study, we faced several logistical challenges but had success in recruiting 32 children in 2018-2019 (16 each in VENT and UC). Based on our current data, the estimated mortality in UC and VENT are respectively, 36% and 25%. Maintaining the mortality rate in UC, a one-sample lower test at significance level $\alpha=0.05$ of a null difference has 80% power to detect a reduction in mortality to 18% in VENT with 33 subjects in VENT.

[figure not shown]

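### Section 11.7 tests for a treatment effect on two measures taken before randomisation, and Section 11 states no marker-against-MRI analysis for Secondary Objective 2

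*Combined protocol and SAP*

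**What the plan says.** Section 11.7 states that "Continuous variables such as optic nerve sheath diameter on admission, heart rate variability patterns, and opening CSF pressure on admission are analyzed using linear models". After allowing for a transformation it continues: "To assess the effect of treatment on outcome we will fit the linear model". The hypothesis tested is β1 = 0, β2 = 0, where these "are the coefficients for the VENT and HPS, respectively". The 95% intervals it promises are for the response mean, not for differences between arms. On the data to be modelled: "We expect $N=128$ across all three arms".

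Table 8 lists optic nerve sheath diameter (ONSD; admission, then daily) and opening CSF pressure (admission) as secondary outcomes under linear regression. Serial ONSD, transcranial Doppler (TCD) and heart rate variability (HRV) go to repeated-measures analysis.

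On timing, Section 3.2.2 places opening CSF pressure at admission only, and Section 8.2.1 says: "A lumbar puncture will be attempted at the time of admission on all children admitted to the PRW". Section 5.3.1 places randomisation after the eligibility screening procedures.

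Secondary Objective 2 in Section 3.1 is to "evaluate and validate biomarkers of increased brain volume" in all children with cerebral malaria whose parents consent to screening. Section 4 confirms that screened children who are not randomised belong to this objective.

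**The concern.** A value recorded before allocation cannot respond to allocation. A treatment test on admission ONSD or opening CSF pressure has no effect to estimate, so a significant result can come only from chance or from arms that were not comparable at entry. The second source matters here because most of the UC arm is not concurrent with the intervention arms.

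The purpose of these markers lies elsewhere. Section 2.3 explains that surrogates are wanted so that an effective treatment could be used without MRI. That calls for setting each marker against the MRI score across the whole range of brain volume. A model with an arm indicator, fitted to children who were mostly selected for a high score, does not do this. Followed as written, the plan would yield a treatment p-value that means nothing for the admission measures and no stated answer to a named secondary objective.

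**Working it through.** **1. The plan's own figure.** UC is 64 (16 randomised in 2018-2019 plus 48 historical, Section 11.5). For HPS, Section 11.7 says "Minimum size in HPS is 32". VENT is 32 in the projected enrolment table in Section 4. The sum is 64 + 32 + 32 = 128, which reproduces the stated N. (That enrolment table itself totals 68 + 32 + 32 = 132, because it allows 4 more UC children in 2023. Section 11.7 gives 21 for VENT if futility is declared.) The 128 therefore includes the historical controls and excludes every screened child without an arm.

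**2. Order of events.** Admission and lumbar puncture come first, then screening with MRI, consent to the trial, randomisation and treatment. Opening CSF pressure is measured once, at the first step. Appendix A shows the first ONSD under the trial-consent column rather than admission, but consent still precedes randomisation. Neither measure can carry a treatment effect.

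**3. What the test can detect.** The significance level for secondary outcomes is not stated; 5% two-sided is assumed. With no true difference, the joint test rejected in 5.0% of 40,000 simulated trials with arms of 64/32/32. For two such measures, assumed independent, the chance of at least one false treatment effect is 1 − 0.95² = 9.8%.

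If the 48 historical children differ from the others by s SD, the UC mean moves by (48/64)s = 0.75s. The documents give no value for s, so a range is shown:

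| Assumed shift s (SD) | Shift in UC mean (0.75s) | Joint test rejects |
|---|---|---|
| 0 | 0 | 5% |
| 0.2 | 0.15 | 10% |
| 0.3 | 0.225 | 18% |
| 0.5 | 0.375 | 43% |

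The comparability check in Section 4 (48 historical against 16 randomised UC children) covered age, sex, coma score, glucose, haematocrit, platelets and outcome. It did not cover ONSD or CSF pressure.

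**4. Children outside the model.** Section 4 gives 57 recruited and 8 randomised in 2018, and 42 screened and 24 randomised in 2019. Screened: 57 + 42 = 99. Randomised: 8 + 24 = 32. Without an arm: 99 − 32 = 67, or 68%. The 48 children screened in 2020 are left out of this count because brain volume could not be assessed that year, so they lack the reference standard.

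**5. Joint test against separate contrasts, for measures taken after randomisation.** This illustration uses one value per child and a true difference of 0.6 SD in one arm only.
- Joint test: overall mean = 32 × 0.6/128 = 0.15. Noncentrality = 64(0.15²) + 32(0.45²) + 32(0.15²) = 8.64 on 2 and 125 degrees of freedom. Power is 74%.
- One contrast with UC: standard error = √(1/64 + 1/32) = 0.217 SD and noncentrality = 0.6/0.217 = 2.77. Power is 79% at 0.05 and 69% at 0.025.

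Over 0.4 to 0.7 SD the ranges are 39-87% (joint), 45-89% (contrast at 0.05) and 34-83% (contrast at 0.025). Power is similar either way. The difference is that a joint rejection does not name the arm.

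**The case against.** Several points on the other side stand.

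- **Pairwise questions.** A reader might infer that the joint test leaves the VENT-UC and HPS-UC questions unanswerable. It does not. With UC as the implied reference, β1 and β2 are those contrasts, so the same model yields both. What is missing is a statement that each will be reported with an interval. The primary VENT-UC test sits in the sequential design of Section 11.6 and does not use this model.
- **HRV.** The quoted sentence also names HRV, but its timing is inconsistent: Section 4 ends it at the initial MRI, while Section 8.3.6 schedules readings through the stay. It is not part of the admission point. Later ONSD values fall under the serial model in Section 11.7.
- **Non-randomised children.** It is tempting to read all 67 as the low-volume comparison group. Section 2.3 reports three children with a real-time score of 6 and a consensus score of 7 in a season when 7 made a child eligible. Section 4 also keeps in this group children whose caregivers declined randomisation. Many of the 67, but not all, would score below 6.
- **Baseline comparison.** Section 11.3 already treats arm differences at baseline as a check on randomisation, which lowers the risk of misreading. But Table 8 lists opening CSF pressure as an outcome, and Section 11.7 states the treatment purpose outright.
- **Historical data.** No section says that ONSD or CSF pressure will be retrieved for the historical controls. Section 2.3 does say that serial ONSD has been collected on all patients since 2013, and the stated N of 128 counts these children. The size of any shift remains an assumption.
- **Flexibility.** Table 8 gives ordinal regression for brain volume, and Section 11.7 admits clinical covariates. Markers could be fitted that way, but the text does not say so and limits N to the arms.

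**Conclusion.** The point holds for admission ONSD and opening CSF pressure: the stated test cannot show a treatment effect, only chance or a control group that was not comparable. It also holds that Section 11 states no marker-against-MRI analysis for Secondary Objective 2 and models only the children in the arms, leaving out 67 of the 99 screened in 2018-2019. That the treatment test is uninformative follows from the order of events alone. The 10-43% false-rejection range rests on an assumed shift of 0.2 to 0.5 SD, a 5% level, and historical children being included with these measurements.

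For continuous measures followed after randomisation the gap is smaller: the contrasts are available from the model but not promised. A reader might conclude that the trial's main comparisons are compromised. The documents do not support that, because the primary outcome has its own test. This should be corrected before analysis, but it does not affect the primary result.

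**What to change.** 1. Remove the treatment test for measures taken only at admission, and for the admission value of serial measures.
2. For Secondary Objective 2, relate each admission marker to the consensus brain volume score on the admission MRI, in all screened children who have both. Keep the ordinal score as the main scale. Add AUC, sensitivity and specificity for a score of 6 or more, each with a 95% confidence interval. Report how many screened children lack the marker or the MRI.
3. For serial ONSD, TCD and HRV after randomisation, report the VENT-UC and HPS-UC coefficients separately with 95% confidence intervals, adjusted for the admission value.
4. Reconcile the two accounts of HRV timing (Sections 4 and 8.3.6), so that it is clear which HRV values fall under items 1 and 3.

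The cost is analysis-plan wording and a little extra analysis. No new data collection is required. The Objective 2 sample will be smaller than the number screened: lumbar puncture is only attempted, the 2020 children have no brain volume score, and Appendix A schedules ONSD as a trial procedure, so some non-randomised children may not have it.
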